8.5.4.3 Secondary Efficacy Endpoint Analysis

The analysis of secondary endpoints is intended to support the secondary objectives of the study. In order to add credibility to the results of key secondary endpoint analyses, an adjustment for multiplicity of endpoints will be applied. Key secondary efficacy endpoints include the percent change from baseline to one and five years on therapy for carotid and aortic vessel wall area, and carotid and aortic vessel wall thickness. The same method of analysis as used for the primary efficacy endpoint will be used for secondary efficacy endpoints. The multiplicity adjustment will be applied as follows: First, secondary endpoints will only be candidates for statistical significance following a statistically significant result for the primary endpoint of two-year percent change in carotid wall area. Subsequently, the p-values from the separate tests of significance of each key secondary endpoint are ranked from smallest to largest. If the largest p-value is

<0.05, then all secondary endpoints will be declared statistically significant. If the largest p-value is ≥ 0.05 , then the next-largest p-value is tested at a significance level of 0.025, and if significant then that endpoint and all remaining endpoints are declared statistically significant. The procedure continues in this fashion, using significance levels of 0.05/3 and so on (Hochberg, 1988).

Additional secondary endpoints will include laboratory evaluations for LDL-C, and other lipoprotein biomarkers at one, two and five years of lomitapide treatment and the correlation of these laboratory evaluations with the change from baseline in MRI parameters of carotid and aortic atheroma. An additional secondary analysis will be performed on atheroma parameters from patients who have discontinued lomitapide therapy and who have a final MRI approximately one year after discontinuing lomitapide. These additional endpoints will not be subject to multiplicity adjustment, with statistical analyses considered to be descriptive.

Lipoprotein biomarkers include:

- Total cholesterol (TC)
- High density lipoprotein (HDL-C)
- Low density lipoprotein (LDL-C)
- Triglycerides (TG)
- Apolipoprotein B (apo B)
- Apolipoprotein A-I (apo AI)
- Lipoprotein (a) (Lp(a))
- Apolipoprotein C-III (Apo C-III)
- LDL sub-fractions by NMR technology

As a supportive analysis to the primary endpoint results, the percent change from baseline to one year on lomitapide therapy will be analyzed in the same manner as the primary time-point of two year MRI data. To control for potential multiplicity effects, statistical significance of the one year data will only be claimed if the primary two year data is statistically significant.

The exploratory analyses to look at the potential impact of covariates as described above will also be performed for key secondary endpoints.

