8.5.1 Efficacy Endpoints

The primary objective of the study is to assess the change in carotid atheroma as reflected by carotid vessel wall area on MRI scanning following two years of treatment with lomitapide. The endpoint used to address this objective will be the percent change in carotid vessel wall area from baseline to two years on lomitapide therapy, where percent change is calculated as $100 * \{WA(24) - WA(0)\} / WA(0)$. WA(x) denotes wall area at either baseline (x=0) or 24 months (x=24). The mean area obtained from the left and right carotid arteries will be used in the primary analysis; additional analyses will consist of individual results from the left and right arteries separately. Refer to Section 8.5.2 for the derivation of wall area measurements.

The secondary objectives of the study are:

- To assess the changes in atheroma burden as reflected by changes in average aortic vessel wall area, average aortic and carotid vessel lumen area, total vessel area, wall thickness, normalized wall index and standard deviation of wall thickness on MRI following two years of lomitapide treatment compared to baseline.

- To assess the changes in atheroma burden as reflected by changes in average aortic and carotid vessel wall area, lumen area, total vessel area, wall thickness, normalized wall index and standard deviation of wall thickness following one year and five years of lomitapide treatment compared to baseline.
- To assess changes in LDL-C and other lipoproteins at one, two and five years of lomitapide treatment compared to baseline and the correlation of these laboratory evaluations with the change from baseline in MRI parameters of carotid and aortic atheroma.

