8.5.4.4 Exploratory Endpoint Analysis

The analysis of exploratory endpoints will be descriptive only. Exploratory endpoints will consist of lumen area, total vessel area, standard deviation of wall thickness and the normalized wall index, at baseline, one, two, five years and one year post discontinuation of lomitapide if available. Exploratory endpoints will also include laboratory evaluations of biomarkers for inflammatory and cardiovascular processes. Correlation analysis will be performed between changes in these potential biomarkers and the change from baseline in MRI parameters of carotid and aortic atheroma.

The major plaque compositional features will include the necrotic lipid area, fibrous cap thickness and calcium area. These are quantified as either present or absent by subjective analysis, and will be analysed as categorical data through summary statistics of number and percentage of positive and negative results. These plaque composition analyses will be performed if sufficient data exist with respect to both the size of the plaques as well as frequency.

Inflammatory and cardiovascular biomarkers include:

- High sensitivity C reactive protein (hs-CRP)
- Serum amyloid A (SAA)
- Soluble Inter-cellular Adhesion Molecule-1 (sICAM-1)
- Interleukin 6 (IL-6)
- Lipoprotein Associated Phospholipase 2 (LpPLA2)
- Soluble Vascular Cell Adhesion Protein 1 (sVCAM-1)
- Soluble E-selectin (sE-selectin)
- Soluble interleukin-6 receptor (sIL-6 Receptor)
- Fasting glucose and insulin and calculate HOMA (Homeostasis Model Assessment)

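### Section 8.5.4.3 provides no multiplicity-controlled test for the two-year aortic wall area and wall thickness endpoints, and states two rules for one-year carotid wall area that can conflict

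*Protocol*

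**What the plan says.** **Objectives.** Protocol sections 3.3, 7 and 8.5.1 give as the first secondary objective the two-year "changes in average aortic vessel wall area, average aortic and carotid vessel lumen area, total vessel area, wall thickness, normalized wall index". The SD of wall thickness is also part of it. The second secondary objective covers one and five years.

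**Adjusted family.** Section 8.5.4.3 first sets the gate: "secondary endpoints will only be candidates for statistical significance following a statistically significant result for the primary endpoint". It then defines the family: "Key secondary efficacy endpoints include the percent change from baseline to one and five years on therapy for carotid and aortic vessel wall area", plus carotid and aortic wall thickness. Within it, "the p-values from the separate tests of significance of each key secondary endpoint are ranked from smallest to largest". If the largest is not below 0.05, "then the next-largest p-value is tested at a significance level of 0.025", and so on by Hochberg's method.

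**Second statement on year one.** At the end of the same section, as support for the primary endpoint, "the percent change from baseline to one year on lomitapide therapy will be analyzed in the same manner as the primary time-point". Multiplicity is addressed there by one condition: "statistical significance of the one year data will only be claimed if the primary two year data is statistically significant".

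**Other lists.** The additional, unadjusted secondary endpoints in 8.5.4.3 are lipoproteins, their correlations with MRI change, and scans after stopping lomitapide. Section 8.5.4.4, which is descriptive only, says: "Exploratory endpoints will consist of lumen area, total vessel area, standard deviation of wall thickness and the normalized wall index". This covers baseline and all three follow-up years. Section 8.5.2 also calls these four measures exploratory.

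**The concern.** The section says that it supports the secondary objectives and that the adjustment lends credibility to the key secondary results. Three things work against that.

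- The secondary MRI endpoints measured at the primary time point, aortic wall area and wall thickness at two years, are missing from the family in which claims are allowed. No other list holds them.
- One hypothesis, one-year carotid wall area, is covered by a Hochberg step in one paragraph and by the gate alone in another. Which paragraph the analyst follows can decide whether a claim is made.
- Four measures change tier between the objectives and the analysis sections.

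A protocol may leave detail to the SAP. Here, though, it fixes a family and two rules that do not agree with each other or with its own objectives, and an SAP would have to overrule one of them.

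**Working it through.** **1. Where each endpoint sits.**

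| Measure | Year 1 | Year 2 | Year 5 |
|---|---|---|---|
| Carotid wall area | key secondary, and the separate one-year rule | primary | key secondary |
| Aortic wall area | key secondary | no list | key secondary |
| Carotid wall thickness | key secondary | no list | key secondary |
| Aortic wall thickness | key secondary | no list | key secondary |
| Lumen area, total vessel area, SD of wall thickness, normalized wall index | secondary (objectives), exploratory (8.5.2, 8.5.4.4) | same conflict | same conflict |

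The family as written has 4 measures × 2 time points = 8 tests. Three two-year tests are in no list.

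**2. The two rules for one-year carotid wall area.** Hochberg levels are 0.05/k, where k is the rank counted from the largest p-value. With eight tests they run from 0.05 down to 0.05/8 = 0.00625. The later rule names no level beyond the gate, so used alone it means 0.05.

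Example: the primary is significant, one-year carotid wall area has p = 0.03 and the other seven have p = 0.20. Under Hochberg the smallest p-value faces 0.00625, so there is no claim. Under the gate alone, 0.03 is below 0.05, so there is a claim.

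**3. Family-wise error if the later rule is the sole control for that endpoint.** Eight equicorrelated normal test statistics, all nulls true, primary gate taken as passed, 2,000,000 simulated sets for each correlation:

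| Correlation (assumed) | Hochberg alone | Hochberg, with one-year carotid wall area also claimable at 0.05 |
|---|---|---|
| 0 | 4.9% | 9.1% |
| 0.3 | 4.6% | 8.5% |
| 0.5 | 4.0% | 7.6% |
| 0.7 | 3.1% | 6.5% |

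Hand check at correlation 0, with seven tests at 0.00625 and one at 0.05: 1 − 0.95 × 0.99375^7 = 9.1%.

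**4. Years one and five in one step-up.** At worst the four five-year p-values take the four highest ranks, so the largest one-year p-value faces 0.05/5 = 0.01. A one-year p below 0.00625, or all four below 0.01, is therefore significant whatever year five shows. Between those bounds the answer can depend on year five. With four one-year p-values of 0.03 and four five-year p-values of 0.20, pooled Hochberg rejects nothing (0.03 against 0.01). The four one-year tests as their own family would all be rejected (0.03 against 0.05).

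**5. Size of the repair.** Adding the three two-year tests gives 8 + 3 = 11, and the strictest level becomes 0.05/11 = 0.00455.

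The plan's own planning figure reproduces: with a 10% change and SD 22%, the one-sample t-test has 80.05% power at n = 40 and two-sided 0.05. With the same inputs, power is 50.1% at 0.00625 and 45.6% at 0.00455. Applying the two-year carotid figures to other endpoints is an assumption. Hochberg alone with 11 tests keeps error at 4.9% to 2.9% over correlations 0 to 0.7.

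**The case against.** **The later one-year rule is only a necessary condition.** It says when a claim may not be made and repeats the gate, so gate and Hochberg can both apply. This stands: the two paragraphs are compatible on that reading, and it would go too far to call them irreconcilable. But the sentence is offered as the multiplicity control for the one-year data and does not mention Hochberg, so the looser reading is open. The error rates above belong to that reading only.

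**The error rates are a worst case.** Independence is the least plausible assumption for repeated measures on the same vessels, and if the primary null is also true the gate caps overall error at 5%. Both points are right. The figures are conditional on a passed gate, which is the situation in which secondary claims are made, and the excess remains at correlation 0.7.

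**The two-year endpoints are not lost.** They are secondary in 8.5.1, and 8.5.4.3 applies the primary method to secondary endpoints, so they would be analysed and estimated. A reader might infer that they can support no conclusion at all, and the text does not bear that out. What is missing is a place in the adjusted family. Reading the key list as open-ended does not help, because Hochberg's divisor then has no fixed number of tests.

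**Pooling years one and five is a legitimate choice.** This stands. It does not inflate error, and a reader who infers that no one-year claim is possible before year five would be wrong, as step 4 shows.

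**The tier conflict is labelling.** Largely so: none of the four measures is in the adjusted family, and no planned adjusted claim changes.

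**Conclusion.** The point holds in three parts.

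- **(a)** Two-year aortic wall area and two-year carotid and aortic wall thickness, part of the first secondary objective, are in none of the analysis lists. No multiplicity-controlled claim is provided for them at the primary time point.
- **(b)** One-year carotid wall area is subject to two statements that can conflict. If the gate alone is used, family-wise error is about 6.5% to 9.1% instead of at most 5%. This assumes eight true nulls, a passed gate and correlations of 0.7 to 0.
- **(c)** Four measures are secondary in the objectives and exploratory in the analysis sections.

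The pooling of years one and five is a design weakness and not an error: one-year results that are not already decisive stay open until the five-year scans, three years after the two-year ones.

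A reader might also infer from the three aortic segments in 8.5.2 that the family really has 16 tests. The objectives speak of an average aortic wall area, and nothing says that segments are tested separately.

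The primary analysis and the sample size are not affected.

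**What to change.** - In 8.5.4.3, list every key secondary test with its measure and time point. Add two-year aortic wall area and two-year carotid and aortic wall thickness, and define aortic wall area as the average named in the objectives, so that the number of tests is fixed at 11.
- Delete the separate one-year rule, or add that a one-year carotid wall area claim also requires the Hochberg step.
- Put lumen area, total vessel area, SD of wall thickness and normalized wall index in one tier throughout 3.3, 7, 8.5.1, 8.5.2 and 8.5.4.4.
- Optional: close a year-one and year-two family at the two-year analysis and handle year five separately, with the error control across the two families stated. Five-year tests need not be made conditional on every earlier test being significant. That is a debatable trade-off and could demote a stated secondary objective.

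The change is to wording and needs no further patients or scans. Its price is the larger family: the strictest level falls from 0.00625 to 0.00455, and power at that level from about 50% to about 46% under the planning assumptions.

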8.5.4.4 Exploratory Endpoint Analysis

The analysis of exploratory endpoints will be descriptive only. Exploratory endpoints will consist of lumen area, total vessel area, standard deviation of wall thickness and the normalized wall index, at baseline, one, two, five years and one year post discontinuation of lomitapide if available. Exploratory endpoints will also include laboratory evaluations of biomarkers for inflammatory and cardiovascular processes. Correlation analysis will be performed between changes in these potential biomarkers and the change from baseline in MRI parameters of carotid and aortic atheroma.

The major plaque compositional features will include the necrotic lipid area, fibrous cap thickness and calcium area. These are quantified as either present or absent by subjective analysis, and will be analysed as categorical data through summary statistics of number and percentage of positive and negative results. These plaque composition analyses will be performed if sufficient data exist with respect to both the size of the plaques as well as frequency.

Inflammatory and cardiovascular biomarkers include:

- High sensitivity C reactive protein (hs-CRP)
- Serum amyloid A (SAA)
- Soluble Inter-cellular Adhesion Molecule-1 (sICAM-1)
- Interleukin 6 (IL-6)
- Lipoprotein Associated Phospholipase 2 (LpPLA2)
- Soluble Vascular Cell Adhesion Protein 1 (sVCAM-1)
- Soluble E-selectin (sE-selectin)
- Soluble interleukin-6 receptor (sIL-6 Receptor)
- Fasting glucose and insulin and calculate HOMA (Homeostasis Model Assessment)

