8.5.2 Efficacy Measurements

Carotid and aortic plaque burden will be measured as follows: The fat-suppressed black-blood fast spin echo proton density or T2 weighted images will be analyzed with a semi-automated algorithm to segment the inner lumen boundary and outer vessel wall area at the adventitial layer. Subtraction of the lumen area from the outer vessel wall area provides the vessel wall area. Mean carotid vessel wall area is obtained from the analysis of the serial images that cover the bilateral common carotid arteries. Mean aortic wall areas are obtained in three segments: the ascending aorta, the descending thoracic aorta and descending abdominal aorta. Average vessel wall area (mm^2) = sum of wall area for each slice/total number of slices will be computed. The images will be matched for locations across visits using anatomical landmarks.

Total carotid plaque burden derived from MRI is reported from the individual carotid arteries as well as the average vessel wall area of both left and right carotid arteries.

Exploratory endpoints will include the lumen area, total vessel area, standard deviation of wall thickness and the normalized wall index. Mean wall thickness measurements are obtained using the centerline method and are obtained for each slice separately and averaged. Measurements are obtained from both carotids and the aortic segments described previously for wall area measurements. The normalized wall index (NWI) is the ratio of the vessel wall area divided by the total vessel area.

Carotid Plaque Composition - The axial multi-contrast proton density (PD), T1 and T2 weighted) black-blood images obtained in the carotid will be analyzed with a semi-automated algorithm to determine inner and outer vessel wall boundaries as well as major plaque compositional features determined from the contrast patterns across each of the

three images acquired at the same location. The major features include the necrotic lipid area, fibrous cap thickness and calcium area. These are quantified as either present or absent by subjective analysis.

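### Four MRI measures are both secondary and exploratory, and the first Hochberg step declares more endpoints significant than it ranks

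*Protocol*

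**What the plan says.** **Status of the four measures.** Sections 3.3, 7 and 8.5.1 of the protocol carry the same secondary objectives. The two-year objective covers aortic wall area and "average aortic and carotid vessel lumen area, total vessel area, wall thickness, normalized wall index and standard deviation of wall thickness on MRI". The next objective covers carotid and aortic wall area and "lumen area, total vessel area, wall thickness, normalized wall index and standard deviation of wall thickness following one year and five years". Section 8.5.2, which directly follows 8.5.1, says: "Exploratory endpoints will include the lumen area, total vessel area, standard deviation of wall thickness and the normalized wall index". Section 8.5.4.4 repeats this: "Exploratory endpoints will consist of lumen area, total vessel area, standard deviation of wall thickness and the normalized wall index". It adds: "The analysis of exploratory endpoints will be descriptive only".

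**Multiplicity rule (8.5.4.3).** Secondary endpoints become candidates for significance only after a significant primary result. The key family is defined thus: "Key secondary efficacy endpoints include the percent change from baseline to one and five years on therapy for carotid and aortic vessel wall area", and wall thickness in the same two vessels. Then "the p-values from the separate tests of significance of each key secondary endpoint are ranked from smallest to largest". If the largest p-value is below 0.05, "then all secondary endpoints will be declared statistically significant". At the next step, conclusions extend to that endpoint and the remaining ones.

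**Other statements in 8.5.4.3.** Secondary efficacy endpoints are analysed by the primary method, with no restriction to key ones. A further group of additional secondary endpoints is unadjusted and descriptive. It holds lipoprotein results, their correlation with MRI changes, and MRI after stopping lomitapide.

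**The concern.** There are two linked problems.

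First, the same result cannot be both secondary and exploratory here, because status decides the analysis. As secondary efficacy endpoints, lumen area, total vessel area, normalized wall index and standard deviation of wall thickness would each get the one-sample t-test of 8.5.4.2. As exploratory endpoints they are only summarised. The statistical analysis plan is not at hand, but it could not settle this without departing from one part of the protocol.

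Second, the first Hochberg step concludes about a wider set than it ranks. A reader who takes the sentence at face value could report as significant an endpoint whose own p-value never entered the procedure. Section 8.5.4.3 introduces the adjustment to make the key secondary results more credible, and a conclusion that spills beyond the ranked family works against that purpose.

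**Working it through.** The protocol gives no endpoint count and no error rate for these measures, so there is no planned figure to reproduce. The check is an enumeration and a comparison of sections.

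**1. Count the secondary MRI endpoints in 8.5.1** (aorta taken as one vessel; each listed measure taken to apply to both vessels).
- Two years: aortic wall area, plus five measures in two vessels: 1 + 5 × 2 = 11.
- One and five years: six measures in two vessels at two times: 6 × 2 × 2 = 24.
- Total: 11 + 24 = 35.

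**2. Locate each one in the analysis sections.**

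| Endpoints | Count | Placed by 8.5.4.3 or 8.5.4.4 |
|---|---|---|
| Wall area and wall thickness, two vessels, one and five years | 2 × 2 × 2 = 8 | Key secondary, Hochberg |
| Lumen area, total vessel area, normalized wall index, SD of wall thickness, two vessels, one, two and five years | 4 × 2 × 3 = 24 | Exploratory, descriptive |
| Aortic wall area, carotid wall thickness and aortic wall thickness at two years | 3 | Nowhere |

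8 + 24 + 3 = 35, so the list is complete. Section 8.5.2 measures the aorta in three segments. If these were analysed separately there would be four vessel sites, and the 24 would become 4 × 4 × 3 = 48.

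**3. Read the first Hochberg step sentence by sentence.** The ranked list holds the 8 key p-values. The largest p-value is therefore the largest of those 8. The next step, with its reference to remaining endpoints, also fits that list. Only the conclusion of the first step, and the gate sentence before it, speak of secondary endpoints without the word key.

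**4. Apply the conclusion literally.** Suppose that the primary endpoint is significant and all 8 key p-values are below 0.05.
- The three unassigned two-year endpoints are secondary in 8.5.1 and excluded by no descriptive clause. They would be declared significant whatever their own p-values.
- The 24 disputed results would follow only if they are also taken as secondary, against 8.5.4.4.
- The additional secondary endpoints would be caught by the wording too, although the same section calls them descriptive. The literal reading therefore conflicts with the section itself.

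**5. Check the corrected rule.** Hochberg on the 8 key endpoints, all null, with equally correlated normal statistics (100,000 simulations; correlations assumed), gives a familywise error of 4.9%, 4.0% and 2.6% at correlations 0, 0.5 and 0.8. With the word key restored, the procedure holds its level under these assumptions.

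**The case against.** The strongest reply is that this is a dropped adjective. Only key p-values are ranked, the next step refers back to the ranked list, and Hochberg's procedure can reject only hypotheses that it ranked. Everything secondary is gated on the primary result, and 8.5.4.4 makes the four measures descriptive. As a reading of intent this stands. It does not settle the status of the four measures, because 8.5.4.3 applies the primary method to secondary efficacy endpoints without restriction, and its list of descriptive additional endpoints does not name these measures at one, two and five years. Nor does it give the three two-year endpoints a place.

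A reader might go further and infer that 24 uncontrolled results can be claimed, at a familywise error far above 5%. For 24 null tests each at 0.05, the chance of at least one false positive is 1 − 0.95^24 = 71% if independent, and by simulation about 46% at correlation 0.5 and 24% at 0.8. The documents do not support attaching such a figure:
- It assumes 24 separate claims at 0.05, whereas 8.5.4.4 plans description only.
- It ignores the gate. If nothing changes at all, any secondary claim first needs a false-positive primary result, which is held at 5%.
- The literal mechanism is a different one. With all 8 key endpoints null, all 8 p-values fall below 0.05 in 0.00% (correlation 0) to 0.5% (correlation 0.8) of simulated trials.
- If the primary effect is real, a state with all 24 null is hard to sustain. Section 8.5.2 defines wall area as outer area minus lumen area, so on the absolute scale mean lumen area and mean total area cannot both stay fixed while mean carotid wall area changes.
- The correlations are assumptions, not protocol figures.

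**Conclusion.** The contradiction in status is certain: four measures, 24 of the 35 secondary MRI endpoints, have two incompatible statuses across five sections. The overreach in the first Hochberg step is a defect of wording. Taken literally, it reaches at least the three unassigned two-year endpoints, and in the worst case the four disputed measures as well. The literal reading would matter mainly when the primary and key endpoints truly change, which is the result the sponsor hopes to report. The context indicates that only key endpoints were meant, so the point concerns which claims the protocol permits, and no inflated error rate is asserted. The counts rest on treating the aorta as one vessel and applying each listed measure to both vessels.

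**What to change.** 1. Give lumen area, total vessel area, normalized wall index and SD of wall thickness one status in 3.3, 7, 8.5.1, 8.5.2 and 8.5.4.4, consistent with the descriptive analysis already planned. They can be exploratory throughout, or be named among the additional secondary endpoints that 8.5.4.3 makes descriptive and unadjusted.
2. In the first Hochberg step of 8.5.4.3, insert *key* before *secondary endpoints*.
3. Assign two-year aortic wall area and two-year carotid and aortic wall thickness explicitly, either to the key Hochberg family, which would then hold 8 + 3 = 11 endpoints, or to the descriptive, unadjusted endpoints.
4. State that, beyond the primary and key secondary endpoints, no endpoint will be declared statistically significant.

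The cost is wording only: no extra patients, scans or analyses. The sponsor gives up any significance claim on the four measures, which it already plans to analyse descriptively. If the three two-year endpoints join the key family, the later Hochberg thresholds become somewhat stricter; if they become descriptive, no claim is made on them.
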